We will perform an unmasked, randomized controlled trial comparing yoga and mindfulness impact on 1) treatment response 2) level of treatment required 3) pain, activity and quality of life for patients with IC/BPS compared to standard care alone as recommended by the AUA (Table 1). The target population will be those patients with IC/BPS who are cared for by the urogynecology, gynecology and urology specialties. After obtaining informed consent, women will be randomized to either yoga & meditation + Standard of care compared to Standard of care alone. Masking is not possible with this study design, as participants randomized to the yoga/mindfulness versus standard of care will clearly know their treatment arm.

4. Inclusion and Exclusion Criteria

4.1 We will recruit patients who present with IC/BPS per the AUA definition. To confirm the diagnosis of IC/PBS, We will also administer the O'Leary-Sant Interstitial cystitis Symptom Index and Problem Index to determine if patients are candidates for the study. We will also require that they have a physical exam performed in the past 2 years. As documented by others, a domain score of >6 will indicate applicability for enrollment in either symptom or problem domain^{xi}. Additional inclusion criterion include: evidence of an absent UTI (e.g. negative urine

PROTOCOL TITLE: MYPAICE: Mindfulness and Yoga for Pain with Interstitial Cystitis Evaluation

dipstick, a negative urinalysis or urine culture) within 2 months of enrollment as well as ability to speak and understand English or Spanish. We will recruit only patients who will be undergoing first-line and second-line treatment, as defined by AUA and who have not made treatment changes to their regimen in the past 4 weeks.

Patients will be excluded if they have:

- unevaluated hematuria,
- a history of recurrent urinary tract infection (UTI), as defined by AUA criteria as >2 culture-proven UTIs in 6 months or 3 UTIs in one year within the last 5 years,
- urinary retention, defined as a post-void residual (PVR) of >150 mL confirmed by bladder scan or catheterization,
- a history of augmentation cystoplasty or urinary diversion,
- a history of cyclosporine A use
- a history of pelvic radiation or chemotherapy in the past 2 years
- history of radiation induced cystitis
- if patients are currently pregnant or lactating or planning on becoming pregnant in the next 3-4 months

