7.1 The **primary endpoint** of our study is to determine the 3 month Global Response Assessment (GRA) in patients who perform yoga & mindfulness + Standard of care compared to patients who undergo Standard of Care alone, as well as a linear mixed model analysis of the GRA over time. Our **secondary endpoints** include: (i) proportion of patients in each group using accelerated lines of treatment (2-6) based on the AUA guidelines (i) the following validated questionnaires:), O'Leary-Sant Symptom and Problem Index (OSPI/OSCI), patient self-efficacy questionnaire (PSEQ-2), the PROMIS- Pain Interference Short Form 6b (PROMIS-PI and a visual analog scale, and the hospital anxiety and depression scale (HADS-A/D) (iii) Cost analysis potentially using, for example, the QALY scale if funds are found to support this.

7.2 We will not have any primary or secondary safety endpoints for which the study will be powered, as the interventions are extremely low risk (mindfulness and yoga).

7.3 Our **exploratory endpoints** are to investigate compliance to mindfulness and yoga treatment. Due to the extremely low-risk nature of therapeutic interventions, we do not have any safety endpoints.

8. Research Setting

8.1 The study will be performed at the University of New Mexico (UNM) Eubank Women's Primary Care Clinic and Sandoval Regional Medical Center (SRMC) Urogynecology clinics. These Urogynecology clinics are dedicated to care of women with pelvic floor disorders such as interstitial cystitis/bladder pain syndrome (IC/BPS), the target population for this study.

PROTOCOL TITLE: MYPAICE: Mindfulness and Yoga for Pain with Interstitial Cystitis Evaluation

8.2 Potential subjects will be recruited in the UNM Eubank and SRMC clinics when they present for care for IC/BPS, either in person or virtually via telephone or Zoom care visits. All patients will have a history and physical taken to determine their study eligibility, as well as a baseline BPIC-SS. Recruitment will take place either in private exam rooms at these clinics or over HIPAA-compliant telephone or Zoom conversation, and informed consent conversations regarding these clinics will take place via the same means.

8.3 There are no other laboratory tests in this trial other than would be routinely collected in the work up of IC/BPS.

8.4 There will not be involvement of any community advisory board.

8.5 There will not be any research conducted outside of the UNM HSC and its affiliates.

9. Resources Available

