Our primary aim is to determine whether the participants assess themselves as improving following the interventions based on the GRA at 3 months. The target population will be patients with IC/BPS who are seeking care. The current recommendation is to advise patients to undergo conservative management with self-care, behavioral modification techniques. If a patient is interested in this and fulfills study inclusion criteria then we will offer her the choice of volunteering for the study. All women will give consent prior to their enrollment, after they have had time to carefully consider whether they want to participate in the study. Research staff and clinicians will obtain consent either in clinic or via zoom. After enrollment, participants will fill out baseline surveys including:)the O'Leary-Sant Symptom and Problem Index (OSPI/OSCI)Patient Self Efficacy Questionnaire-2 (PSEQ-2), Hospital Anxiety and Depression Scale (HADS-A/D), PROMIS- Pain Interference Short Form 6B (PROMIS-PI), and a visual analog scale

In addition to the above outcomes, we will collect patient demographics, medical/surgical history and information regarding their IC/BPS (e.g. time since IC/BPS diagnosis, previous treatments for IC/BPS tried) and patient contact information. Once this information is collected, patients will also fill out an attestation of use, which they will sign/e-sign in REDCap, an affidavit that if they are randomized to mind/body they will use these daily to the best of their ability.

Randomization: Randomization assignment will be generated by computer generated randomization scheme used by appropriate personnel such as a statistician. Participants will be randomized in a 1:1 ratio by a computer generated sequence at enrollment. Randomization assignments will be completed via REDCAP. Randomization will only occur after consent has been obtained and all baseline data has been obtained.

Interventions:

Yoga & mindfulness meditation + Standard of care: Women will be asked to perform mindfulness meditation via a commercially available smartphone app and yoga through an online video tutorial (designed by a Physical Therapist expert in IC/BPS care and designed specifically for IC/BPS patients). Our online tutorial is currently in the process of being formatted however see supplemental materials for yoga flow. Patients will be instructed to perform

PROTOCOL TITLE: MYPAICE: Mindfulness and Yoga for Pain with Interstitial Cystitis Evaluation

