We will track adverse events when patients bring up these events during the course of the study with their providers or study coordinators. Because neither of the studied treatments are experimental or associated with above average risk, we do not anticipate any serious adverse events; nonetheless, these will be tracked. Participants will have access to a 24/7 phone number to reach research or clinical staff with concerns. All adverse events will be recorded and reported to the study PI.

We do not anticipate any conditions that would trigger a suspension or termination of the research.

14. Withdrawal of Subjects

Participants may withdraw from the study at any time without penalty and will continue to receive the clinical standard of care. A subject may be withdrawn from the study without her consent at the discretion of the physician and study staff if they believe she no longer meets study inclusion criteria or if she meets exclusion criteria, or if they believe that it is not in her best interest to continue study participation i.e., desire to undergo surgical treatment. Investigators may withdraw a subject if the subject is not following the study protocol. If a woman is withdrawn from the study either at her own discretion or that of the research staff, she may continue with conservative or surgical management of her IC/BPS in the usual fashion. We will collect a withdrawal Global Response Assessment to use for her progress and will utilize her data up until the time point that she is withdrawn from the study.

To minimize withdrawal from the study, patients will be randomized after they have had what they feel to have been adequate time to consider whether or not they would like to participate in the study and they provide consent. We will document reasons for withdrawal from the study if the participant willingly provides this information. We will report eligibility criteria not met or reasons for declining participation in the study if the participant willingly provides this information. The withdrawal procedure is clearly documented in the study consent.

15. Data Management/Confidentiality

PROTOCOL TITLE: MYPAICE: Mindfulness and Yoga for Pain with Interstitial Cystitis Evaluation

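### Section 14 lets unmasked staff withdraw women for non-adherence or for wanting surgery and ends their data there; if used unequally, this can bias the 12-week GRA comparison in either direction and lose later escalation events

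*Combined protocol and SAP*

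**What the plan says.** Section 14 (Withdrawal of Subjects) gives two grounds on which staff may end participation. One is non-adherence: "Investigators may withdraw a subject if the subject is not following the study protocol". The other is a judgement, not needing the woman's agreement, that continuing is not in her best interest, which the section explains as "desire to undergo surgical treatment". No threshold is given for either.

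After withdrawal, the plan "will utilize her data up until the time point that she is withdrawn from the study". It adds one assessment: "We will collect a withdrawal Global Response Assessment to use for her progress". Where that value enters the analysis is not stated. On reasons, "We will document reasons for withdrawal from the study if the participant willingly provides this information".

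The surrounding text matters:

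- Section 3: "We will perform an unmasked, randomized controlled trial".
- Section 12, interventions: the yoga arm has daily practice and weekly calls described as checking compliance. The control arm's weekly calls are described as monitoring progress.
- Section 12, escalation: higher lines of therapy may be discussed at week 6. Escalation is recorded while a woman is in the study, and the catch-up escalation survey goes to women who have completed it.
- Primary outcome: section 5.3 describes a mixed model of GRA over time, section 12 names the 12-week result, and section 7.1 names both. Section 5.3 also defines responders, and Data Analysis plans chi-square tests for categorical variables and a linear mixed model for the repeated GRA.

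The visible text does not require follow-up after withdrawal, does not state that women are analysed as randomised, and has no rule for a missing 12-week GRA.

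**The concern.** Withdrawal is decided by people who know the arm, and both grounds can be related to what is being compared.

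Non-adherence falls unevenly. A control can breach the protocol, for example by using the video or app or by missing surveys, but cannot miss a daily practice she was never assigned. If poor adherers also respond poorly, removing them raises the observed response in the yoga arm. The surgery ground works through outcome: a woman who wants surgery may be one whose symptoms have not improved. If more such women are removed from the control arm, the observed control response rises and the comparison shifts against yoga.

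Escalation, a secondary endpoint in section 7.1, has a more direct problem. A woman removed before she escalates contributes no event, and the catch-up survey does not reach her. No repeated-measures model is planned for this endpoint. The same record is meant to feed the cost-utility analysis (section 12), so a lost event carries through. Section 14 also leaves open whether the escalation therapies offered at week 6 count as the surgical treatment that can end participation.

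**Working it through.** **The plan's own figure.** Section 5.3 gives 41 per group for a 30-point difference from 26%, with 80% power and alpha 0.05. Reading this as 26% against 56%, two-sided, pooled variance, no continuity correction:

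n = [1.96 × √(2 × 0.41 × 0.59) + 0.842 × √(0.26 × 0.74 + 0.56 × 0.44)]² / 0.30² = 41.0.

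The figure reproduces. This point does not dispute it.

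**Inputs for the illustration.** From the documents: 26% response and 47 randomised per group (section 5.3). Assumed: no true effect (26% in both arms), the share f removed, and the 12-week response r among those removed. The dropout allowances of 15% (section 5.3) and 20-25% (Data Analysis) cover all dropout, so they are not staff-withdrawal rates.

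**Complete-case week-12 comparison.** Observed response among women kept = (0.26 − f × r) / (1 − f). Tests use a normal approximation with the pooled standard error under the null and 47 × (1 − f) women in the affected arm. A false win is a significant result in favour of the arm that lost the women (nominal 2.5%).

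| Removed | f | r | Observed in that arm | False difference | False win |
|---|---|---|---|---|---|
| One arm | 0.05 | 0.10 | 0.255/0.95 = 26.8% | 0.8 points | 3.1% |
| One arm | 0.15 | 0.10 | 0.245/0.85 = 28.8% | 2.8 points | 4.8% |
| One arm, extreme | 0.25 | 0.05 | 0.2475/0.75 = 33.0% | 7.0 points | about 10% |
| Both arms | 0.05 | 0.10 | 26.8% in each | 0 | 2.5% |

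Each one-arm row applies to either arm: removal from yoga favours yoga, and removal from control favours control by the same amount. The first row is 2 to 3 women (0.05 × 47 = 2.35). The extreme row is about 12 (0.25 × 47 = 11.75), with nobody removed from the other arm.

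**What the mixed model would do.** The expected fit was computed for a model linear in time, weekly GRA from week 1 to week 12, 5-25% removed from the yoga arm only, and assumed SDs of 0.6 (intercept), 0.082 (slope) and 0.6 (residual). Share of the complete-case bias that remains:

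| How GRA in removed women departs from the rest | Bias remaining |
|---|---|
| Linear drift, withdrawn at week 4 / 6 / 8 / 10 | 67-69% / 42-45% / 21-24% / 8-9% |
| Constant gap from week 1 | −5% to −14% |
| Plateau reached by week 4 | −35% to +8% |
| Departure only after withdrawal | 100% |

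Negative values are over-correction, up to about a third of the complete-case bias with the opposite sign. The 100% row holds by construction, because no observed value carries the later difference.

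**Escalation.** Suppose 30% escalate in each arm and a quarter of one arm's escalators leave before the event is recorded. Both figures are assumptions. The affected arm then shows 0.30 × 0.75 = 22.5% of all randomised, or 0.225 / (1 − 0.075) = 24.3% of women kept. If a tenth leave, it shows 27.0%, or 0.270 / 0.970 = 27.8%. The plan does not say which denominator applies.

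**The case against.** The strongest reply is that the clause may hardly be used. Its wording is permissive. Women attest that "if they are randomized to mind/body they will use these daily to the best of their ability", and the exploratory endpoints "are to investigate compliance to mindfulness and yoga treatment", which suggests that non-adherence is meant to be measured rather than to lead to removal. At 5% removal the effect is small. This limits the likely size, but the clause and its lack of a threshold remain.

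A second reply is that the mixed model uses every weekly GRA up to withdrawal, so the complete-case figures are not estimates for that analysis. This is correct. But a 12-week result and a responder classification are also planned, with no missing-data rule, and the grid shows that the model's correction depends on trajectories nobody yet knows.

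A third reply is that escalation at week 6 is expressly allowed within the study and recorded by study personnel. That also stands. Loss occurs only for therapy used after withdrawal, and its extent depends on how the surgery ground is read. Finally, section 14 says the consent document also describes withdrawal. Those pages are not visible and may provide for continued contact.

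A reader might infer that the clause tilts the trial towards yoga, because daily practice exists only there. The documents do not support this: the surgery ground can act in the control arm, and the arithmetic is symmetric. Nor do they show that withdrawn women are dropped from analysis altogether, since data before withdrawal are kept, or that women who escalate at week 6 will be withdrawn.

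**Conclusion.** The concern holds in a conditional form. Followed as written, section 14 can end data collection in a way that depends on arm and on outcome, and escalation after withdrawal is not counted. If the clause is used unequally, a week-12 responder comparison can be biased in either direction. If removal is equal, with equal response among those removed, the bias is about zero when there is no true effect.

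The size cannot be fixed from the documents. About 0.8 points at 5% one-arm removal and about 7 points at an extreme 25% are illustrations that rest on assumed removal shares, assumed response among those removed, no true effect and a complete-case test. They are not bounds or forecasts. The mixed model cannot be relied on as the remedy, because it may leave, remove or over-correct the bias.

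This should be fixed, with medium confidence: the mechanism is in the text, the frequency is unknown, the consent pages are unseen, and the repair is cheap.

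**What to change.** 1. In section 14, separate stopping the assigned programme from leaving the study. Record non-adherence and escalation without ending data collection.
2. Continue the remote GRA and the escalation record to week 12 for every randomised woman who has not withdrawn consent.
3. Extend the section 12 catch-up escalation survey to withdrawn women.
4. State in Data Analysis that all randomised women are analysed in their assigned arm, and that the withdrawal GRA is entered at the week it was taken, not as a 12-week value.
5. Reconcile the surgery ground in section 14 with the week-6 escalation option in section 12, without changing clinical care, and check that the consent text agrees.

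Counting a missing 12-week GRA as non-response could be one sensitivity analysis. It gives 0.26 − f × r per arm, which is itself biased, so it does not replace follow-up.

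The cost is an amendment to section 14, two sentences in Data Analysis and a few extra remote surveys, since contact is already weekly and remote. Keeping non-adherent women may make the estimated effect smaller.

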5.3 Sample size calculation: The primary outcome for this study is a linear mixed model of GRA variation over time. Weekly GRA and O'Leary-Sant values will be obtained on all participants. We will then further characterize patients as either treatment responder or non-responders, with treatment response defined as "moderate (+2)" or "marked (+3)" improvement on the GRA. We used previously reported outcomes from an RCT regarding impact of medication on ICBPS symptoms.

Given that we will be performing a linear mixed model, we powered our study to detect a 30% change in treatment response between groups on the GRA, with baseline response rate of 26%. We require 41 participants/group (total N=82) to obtain 80% power ($\alpha=0.05$), assuming an effect size of 0.85. Allowing for a dropout rate of 15%, we aim to randomize 94 women (47/group). We will be able to recruit the required number of participants. We see 12-15 new patients with ICBPS per month and should

be able to adequately recruit 6-7 patients/month, allowing us to meet the necessary sample of patients within 14 months of study initiation. Despite COVID-19, we still continue to care for this number of patients. The study has maximized digital & phone contact and minimized in-person contact. We foresee that we should meet our recruitment aims despite the pandemic's restrictions.

6. Study Timelines

6.1 Based on current clinic volume in the UNM division of the Urogynecology, from which we are recruiting, we estimate that recruitment of 60-120 patients will be feasible over approximately 2-3 years. Per chart review, the urogynecology division sees patients who meet criteria for this study at the rate of 10-20 per month. Assuming that approximately 25% of patients will agree to study participation (due to issues of time commitment and eligibility criteria), we believe that we will be able to recruit an appropriate number of patients in approximately 2-3 years. We believe that an additional 3 months will be needed for follow up data. We anticipate that data analysis and manuscript writing will take an additional 6-9 months.

7. Study Endpoints

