Research Experience: The Urogynecology Division at UNM has a strong history of conducting high quality research and collaboration with other investigators in the US and abroad, and has consistently met or exceeded recruitment goals on time. We have been members of the NICHD-sponsored Pelvic Floor Disorders Network (PFDN), and have met recruitment goals with high rates of follow-up and accurate data collection. In addition to PFDN research, [name] has mentored and has been the PI on multiple clinical trials and contributes multiple publications in peer-reviewed journals. Her Curriculum Vitae is attached.

Our group is well versed in the importance of adherence to protocols, timely completion of regulatory requirements, effective recruitment strategies, and the importance of the inclusion of minority subjects. Research is integral to all aspects of Divisional work; importantly, all members of the clinical team participate in research efforts. There are weekly research meetings to discuss the progress of the ongoing studies within the department, and it is an excellent forum to ensure that all involved are adequately informed of their duties, of the protocol, and of the procedures.

We do not anticipate that emergency care will be needed for this study; the urogynecology physicians are available on a 24 hour basis, 7 days per week for their patients requiring emergency care.

10. Prior Approvals

The only approval prior to commencing research will be with [name], PFPT. She is a certified yoga teacher and a pelvic floor physical therapist with extensive background in making online yoga tutorials. She is designing this yoga sequence for our study (see supplemental materials). This study was presented to [name] for approval, and the signed Departmental Review Form can be found in the “Supporting Documents” Section.

This study does not include ionizing radiation, biological specimens, or drugs.

11. Multi-Site Research

This is not a multi-site research study.

12. Study Procedures

This non-blinded randomized control trial will be conducted at the UNM Eubank clinic and SRMC Urogynecology clinic. We will recruit participants and plan to randomize approximately 60-120 participants from these sites.

Collaborating investigators will be members of the urogynecology division at UNM HSC.

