Data Analysis: Between and within group differences will be evaluated using chi-square analysis as deemed appropriate by the statistician involved in study analysis (e.g. Fisher's Exact test for non-normal distributions of categorical variables and T-test for continuous variables). Differences between groups will be evaluated using Chi-square analyses for categorical variables as deemed appropriate by the statistician involved in study analysis (e.g. Fisher's Exact test for non-normal distributions). T-tests will be utilized for continuous variables, with comparison by Mann Whitney U for non-normal distributions. Within-group differences over time will be analyzed using the McNemar's test. If any baseline differences exist between the groups, a regression or multivariable analysis will determine the contribution of these differences to observed differences between groups. As the GRA and O'Leary-Sant will be collected more frequently, we plan to analyze these results with linear mixed models analysis.

Power Analysis: Power analysis was performed based on previously reported means and standard deviation from treatment effect based on GRA. We assumed that 41 patients in each arm (total 82) would be required to find a difference of 30% between group's pain scores (the primary outcome) with 80% power and alpha of 0.05. In order to achieve power we will need a total of 82 patients. Assuming an approximate 20-25% dropout or loss to follow-up rate, we will plan to randomize approximately 60-120 patients.

13. Provisions to Monitor the Data to Ensure the Safety of Subjects

A DSMB will not be monitoring safety of these procedures as the study risks are low. The intervention arm includes mindfulness and yoga, both of which have been shown to be low-risk interventions with minimal adverse events^{xix}. The control group will undergo standard of care treatments. Theoretically, there could be increased muscle soreness noted in patients in yoga treatment arm. There are no documented adverse events with mindfulness practice.

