Participants will be given a de-identified study subject number. Data collection sheets and questionnaires will contain the subject number. No other patient identifiers will be collected on study forms. PHI including patient name, date of birth, phone number, and medical record number will be collected to track appointments and ensure patient follow-up. The data collection, HIPAA and consent forms will be maintained in a locked file cabinet in the locked Eubank research office. A separate folder will be designated for each participant. PHI will not be entered into the study database. The link between PHI and study IDs will be kept on a password protected computer on a secure UNM OBGYN department server.

The study database does not include sensitive information or information requiring additional protection.

Study binders will be kept in a locked cabinet in the research administrative area. In order to further ensure patient confidentiality, the identifying information will be kept separately from the numbered study files in a locked cabinet.

Electronic data entry will be performed on REDCAP, using the de-identified subject study number. The electronic data and subject link will be encrypted, password protected, and stored on the secure UNM OBGYN department server. This server's electronic security is monitored / maintained by the Health Sciences Library and Informatics Center (HSLIC). A REDCAP database will be created to collect, store and manage the data. REDCAP databases are reposed securely and all data entered is de-identified. The REDCAP database is only accessible using an individual unique login and password and access is only provided to co-investigators. Access is restricted to co-investigators and research staff and will be protected using the unique REDCAP login and password provided to each co-investigator.

Access to the files and REDCAP will be restricted to research personnel and Investigators and will be locked or protected using the unique REDCAP login and password provided to each co-investigator. The data will be stored for 5 years after completion of analysis and then will be destroyed.

A Certificate of Confidentiality will not be used to protect data from forced release. No identifying or study related data will be transported to outside locations. There will be no audio or video recordings or photographs taken.

16. Data and Specimen Banking

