We do not intend to share study progress with participants while the study is underway as not to introduce bias. We do not intend to seek out study participants to disseminate information once the study is complete. Women who are interested in the results will be provided the information where to read the manuscript once it is published. Study results for individual participants will not be shared.

28. Inclusion of Vulnerable Populations

N/A. There will not be any vulnerable populations included in this study.

29. Community-Based Participatory Research

N/A. There will be no involvement of the community in this research.

30. Research Involving American Indian/Native Populations

N/A. This research does not specifically target this population. If an American Indian woman is a candidate for the study, she will be offered participation if she is able to speak/read/write in English or Spanish.

31. Transnational Research

N/A. This study is domestic.

32. Drugs or Devices

N/A. There is no drug or device utilized in this study.

33. Principal Investigator's Assurance

By submitting this study in the Click IRB system, the principal investigator of this study confirms that:

- The information supplied in this form and attachments are complete and correct.
- The PI has read the Investigator's Manual and will conduct this research in accordance with these requirements.
- Data will be collected, maintained and archived or destroyed per HSC Data Security Best Practices, including:

1. **Best Practice for data collection** is for it to be directly entered onto a data collection form that is in a secured access folder on an HS drive behind a firewall, or in a secure UNM Data Security approved system such as REDCAP.
2. **Data collection of de-identified data**, if done in a clinical setting or other setting that does not allow direct entry into a secured system, may be done temporarily using a personal or university owned electronic storage device or hard copy document. **The important security safeguard is that no identifiers be include if the data is entered or stored using an untrusted device or storage.**

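### No single number to randomise is binding (60-120 against 94) and by-arm results are not withheld during the trial, so low power or a results-driven stop is not excluded, though no such stop is planned

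*Combined protocol and SAP*

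**What the plan says.** **Number to randomise.** The Power Analysis closing section 12 says "we will plan to randomize approximately 60-120 patients", after assuming 20-25% loss. Sections 5.2 and 6.1 and the opening of section 12 give the same range. Section 5.3, assuming 15% dropout, says "we aim to randomize 94 women (47/group"). Both calculations rest on the same evaluable number: "We require 41 participants/group (total N=82) to obtain 80% power". No section says which figure governs or what closes recruitment.

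**Access to results.** Section 12 has assignments made in REDCap, and section 15 has the data entered there. Section 15 adds that "Access is restricted to co-investigators and research staff and will be protected using the unique REDCAP login and password provided to each co-investigator". That section is about confidentiality. It describes no user rights by role and neither grants nor bars reports by arm.

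**Monitoring.** The trial is unmasked (section 3) and has no DSMB (section 13). No interim analysis, efficacy stopping rule or alpha adjustment appears, and section 13 foresees nothing that would suspend or end the research. The one stated limit on knowing progress concerns participants: "We do not intend to share study progress with participants while the study is underway as not to introduce bias" (section 27).

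**The concern.** A trial tested once at 5% needs a sample size that is fixed, or at least ended by something unrelated to the results. Here any total from 60 to 120 complies with the protocol, and a reader of the final report could not tell a planned end from one chosen after seeing the data.

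Two things are at stake:

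- **Power.** The lower half of the range includes totals that cannot deliver the stated 80%.
- **Error rate.** Nothing keeps the emerging difference between arms from the people who decide when to stop recruiting. If that difference did inform the decision, the nominal 5% would no longer hold and the estimated effect would tend to be too large.

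**Working it through.** **1. Reproduce the plan's figure.** Inputs from section 5.3: "we powered our study to detect a 30% change in treatment response between groups on the GRA, with baseline response rate of 26" per cent. Reading the 30% as percentage points gives p1 = 0.26, p2 = 0.56 and mean 0.41. The Power Analysis gives "with 80% power and alpha of 0.05"; sidedness is not stated, and two-sided is used here.

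n per group = [1.960 × √(2 × 0.41 × 0.59) + 0.842 × √(0.26 × 0.74 + 0.56 × 0.44)]² / 0.30²
= [1.363 + 0.558]² / 0.09 = 41.0.

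The 41 per group (82 in total) reproduces.

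**2. Does either recruitment figure follow from 82?**

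- At 15% dropout: 82 / 0.85 = 96.5, so 97. The 94 matches 82 × 1.15 = 94.3, which slightly under-inflates.
- At 20-25% dropout: 82 / 0.80 = 102.5, so 103; 82 / 0.75 = 109.3, so 110.
- The range 60-120 follows from neither dropout figure, and 60 is below the 82 evaluable women required. It does match a feasibility estimate: section 6.1 expects 25% of 10-20 women a month, or 2.5-5 a month, and over 24 months that is 60-120. The documents do not say that this is its origin.

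**3. Power along the range.** With m evaluable per group, power = Φ[(0.30 × √m − 1.363) / 0.662].

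| Randomised | No dropout | 15% | 20% | 25% |
|---|---|---|---|---|
| 60 | 66% | 59% | 56% | 54% |
| 94 | 85% | 79% | 76% | 74% |
| 120 | 93% | 88% | 86% | 84% |

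For example, 60 with no dropout has m = 30: (1.643 − 1.363) / 0.662 = 0.42, so 66%.

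**4. Error rate if recruitment were stopped on a by-arm look.** This is a simulation with no true effect, 1:1 allocation, a normal test statistic and an unadjusted two-sided 1.96, with looks between 60 and 120 randomised. The look schedules are assumptions.

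How many women are still in follow-up at the stop depends on the recruitment rate. Section 6.1 implies 2.5-5 a month and section 5.3 says 6-7. Over three months of follow-up that is 7.5 to 21 women, taken as 8-20. Their results enter the final test but are unknown at the look.

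Total two-sided error, stopping on a significant look in either direction:

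| Still in follow-up | One look at 60 | Every 20 | Every 10 | Every 2 |
|---|---|---|---|---|
| 0 (all outcomes known) | 8.3% | 10.6% | 11.9% | 14.4% |
| 8 | 6.8% | 7.8% | 8.2% | 8.6% |
| 14 | 6.4% | 7.2% | 7.5% | 7.8% |
| 20 | 6.1% | 6.8% | 7.1% | 7.4% |

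If recruitment stops only on a result favouring yoga and mindfulness, total error is about 5.6-6.8% with 8-20 in follow-up, and 6.7-9.7% with none. One analysis at a fixed number gives 5.0%. With none in follow-up, a chi-square simulation on responders at 26% in both arms gives nearly the same values (8.4% to 14.6%).

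**The case against.** **No look is planned.** The documents describe no interim analysis. If recruitment ends because of clinic volume, funding or time, the 5% level holds even within a range. This stands: the inflation is a conditional risk, not a property of the plan.

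**There is a target.** Section 5.3 ties 94 to the power calculation, and 60-120 may be only a feasibility band. This stands in part. The number is not simply left open, but one mention of 94 against four of the range, including the section headed Number of Subjects, does not settle which binds.

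**By-arm viewing is inferred.** A reader might infer from section 15 that all staff can see accumulating outcomes by arm. The text says who may log in and nothing about by-arm views. A reader might also take "There are weekly research meetings to discuss the progress of the ongoing studies within the department" (section 9) to mean that results are reviewed by arm. The passage describes general departmental meetings that keep staff informed of duties, protocol and procedures. What can be said is that nothing prevents by-arm summaries.

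**The 12-week lag dilutes any inflation.** This stands, and it is why 8-14% is not the main figure. In the other direction, GRA is collected weekly, so an early look could draw on partial follow-up. That was not modelled, and the lagged figures could be somewhat low for this reason.

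**Restricting REDCap would not mask the staff.** This also stands. Those who call weekly know each woman's arm anyway.

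**Conclusion.** The point holds in a limited form. The protocol gives two incompatible recruitment figures, states no rule for ending recruitment, and does not withhold by-arm summaries before follow-up ends.

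The firm consequence is power: 60 randomised gives 54-66% depending on dropout, and even 94 gives about 79% at 15% dropout and 74-76% at 20-25%. This rests on 26% against 56% responders and a two-sided 5% test.

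The conditional consequence is the error rate. Were recruitment stopped on an unadjusted by-arm look, 5% would become about 6-9% with 8-20 women in follow-up, or about 5.6-6.8% for a stop only on a favourable result. The 8-14% range applies only if all 12-week outcomes were known at the stop. The number of looks is assumed throughout.

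Two stronger readings are not supported. The documents do not show that anyone will look at results by arm or stop because of them. Nor would limiting by-arm reports remove bias in how outcomes are elicited, escalation is offered or withdrawals are decided, since that comes from the acknowledged lack of masking.

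**What to change.** 1. Replace 60-120 in sections 5.2, 6.1, 12 and the Power Analysis with one target fixed in advance (section 5.3 already gives 94), and state that recruitment ends at that number regardless of results.
2. Choose one dropout figure in place of the present 15% and 20-25%, and restate the power for the chosen target under it. If 80% is to be kept, the arithmetic gives 97 randomised at 15% dropout (98 in whole pairs), 103 at 20% and 110 at 25%.
3. In section 15, limit reports and exports of outcomes by arm to the statistician until the last 12-week GRA is in and the data are locked. Staff keep the individual forms they need for calls and follow-up.

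The cost is a REDCap user-rights setting and a few sentences of protocol text. The small downside is that investigators cannot view by-arm results until the end.
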